3. TRIAL OBJECTIVES

Primary Objective and Endpoint	
Objective	Endpoint
To further assess the safety and toxicity profile of camostat, to support integration into a Phase III trial.	Causality and severity of each adverse event (AE) to camostat.
Secondary Objectives and Endpoints	
Objective	Endpoint
To confirm that the PK profile aligns with the established PK profile for the active metabolite of camostat, 4-(4-Guanidinobenzyloxy)phenylacetic acid (GBPA).	Confirm PK parameters of GBPA as assessed by population estimates from population PK analysis (popPK).
To assess the ability of camostat to reduce the requirement for COVID-19 related hospital admission in community patients with SARS-CoV-2 infection.	Rate of COVID-19 related hospital admission in community patients with SARS-CoV-2 infection.
To evaluate the requirement for supplementary oxygen (non-invasive or mechanical invasive) in patients who have received camostat as treatment for SARS-CoV-2 infection.	Supplementary oxygen-free days at 28 days (from randomisation).
To evaluate the requirement for ventilation in patients who have received camostat as treatment for SARS-CoV-2 infection.	Ventilator-free days at 28 days (from randomisation).
To evaluate efficacy of camostat by effect on COVID-19 related clinical improvement.	
Time Frame: Days 1-28
 
Time to worst point on the scale or deterioration of two points or more (from randomisation) on a 9-point category ordinal scale.
 
9-point category ordinal scale:
 
 0. Uninfected, no clinical or virological evidence of infection 1. Ambulatory, no limitation of activities 2. Ambulatory, limitation of activities 3. Hospitalised – mild disease, no oxygen therapy 4. Hospitalised – mild disease, oxygen by mask or nasal prongs 5. Hospitalised – severe disease, non-invasive ventilation or high-flow oxygen

	
 6. Hospitalised – severe disease, intubation and mechanical ventilation 7. Hospitalised – severe disease, ventilation and additional organ support – vasopressors, renal replacement therapy (RRT), extracorporeal membrane oxygenation (ECMO) 8. Death
Research Objectives and Endpoints	
Objective	Endpoint
[REDACTED]	
 - [REDACTED] - [REDACTED] - [REDACTED] - [REDACTED]
[REDACTED]	
 - [REDACTED] - [REDACTED] - [REDACTED] - [REDACTED]

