6.9 Efficacy

To evaluate efficacy of camostat by effect on COVID-19 related clinical improvement.

Time Frame: Days 1-28

Time to worst point on the scale or deterioration of two points or more (from randomisation) on a 9-point category ordinal scale.

9-point category ordinal scale:

0. Uninfected, no clinical or virological evidence of infection
1. Ambulatory, no limitation of activities
2. Ambulatory, limitation of activities
3. Hospitalised – mild disease, no oxygen therapy
4. Hospitalised – mild disease, oxygen by mask or nasal prongs
5. Hospitalised – severe disease, non-invasive ventilation or high-flow oxygen
6. Hospitalised – severe disease, intubation and mechanical ventilation
7. Hospitalised – severe disease, ventilation and additional organ support e.g. vasopressors, renal replacement therapy (RRT), extracorporeal membrane oxygenation (ECMO)
8. Death

Table 10 Ordinal Scale.

Efficacy population

Patient Number	Randomised Arm (Treatment or Control Arm)	Day 1 Scale	Worst Point on Scale	Deteriorated by more than 2 points (yes/no)	Time to worst point (Days)

Table 11: Summary Table for Secondary Endpoint Data.

Efficacy population

	All	Treatment arm	Control arm

Number of community patients admitted to hospital due to COVID-19			
Total number of patients			
Proportion of patients per arm			
Supplementary oxygen-free days at 28 days			
Number of patients			
Proportion of patients per arm			
Ventilator-free days at 28 days			
Number of patients			
Proportion of patients per arm			

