To evaluate the requirement for ventilation in patients who have received camostat as treatment for SARS-CoV-2 infection.	Ventilator-free days at 28 days (from randomisation).	
Measure Title: Number of ventilator - free days
 
Measure Description: Number of ventilator - free days
 
Time frame: Days 1-28
 
Population description: Patients who received camostat for a minimum of five days (treatment arm) or who either completed up to Day 14 or came off trial at an earlier timepoint due to an endpoint defined reason (e.g. hospitalisation).

		
Information to be presented: Median and range of ventilator free days by treatment arm (provided in Stats report).
 
Measure Title: Time to worst point on the scale or deterioration of two points or more (from randomisation) on 9 point category ordinal scale.
 
Measure Description: Median time and range to worst point on the scale or deterioration of two points or more (from randomisation) on 9 point category ordinal scale
 
Time frame: Days 1-28
 
Population description: Patients who received camostat for a minimum of five days (treatment arm) or who either completed up to Day 14 or came off trial at an earlier timepoint due to an endpoint defined reason (e.g. hospitalisation).

	
5. Hospitalised – severe disease, non-invasive ventilation or high-flow oxygen
 
6. Hospitalised – severe disease, intubation and mechanical ventilation
 
7. Hospitalised – severe disease, ventilation and additional organ support – vasopressors, renal replacement therapy (RRT), extracorporeal membrane oxygenation (ECMO)
 
8. Death
	Information to be presented: Median and range of times to worst point on the ordinal scale (provided in Stats report).
--	--	--

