12.2 Main study findings

The primary outcomes for this trial are safety and adverse events. These will be tabulated by treatment group and by strata/subgroups. Pregnancy, compliance, protocol deviations will also be tabulated in this way.

The majority of secondary outcomes will be reported in the main RAP. The secondary outcomes of number of oxygen-free days, ventilator-free days, and number of days to worst point on the 9-point ordinal scale (see secondary objectives in RAP for definitions) will be reported as median and range for the 28 days of follow up post-randomisation.

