12.3 Transformations

12.4 Outputs

Tabular outputs have been described in the main RAP. The following analyses will be in addition to these tables.

Population: Efficacy population (at least 5 days of camostat/14 days of control)

Medians and range for the following variables will be produced by treatment group:

- Number of oxygen-free days,
- Number of ventilator-free days,
- Number of days to worst point on the 9-point ordinal scale

Kaplan-Meier plots of the following variables will be produced by treatment group:

- Time to worst point on ordinal scale

Plots of daily data will also be produced where this will aid interpretation.

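### The two-point part of the ordinal-scale endpoint has no by-arm time output and a mislabelled flag, and time to worst point has no stated rule for patients who never worsen

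*SAP*

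**What the plan says.** The SAP document consists of a Reporting Analysis Plan (RAP, sections 2 to 8) and the SAP proper as its appendix (sections 10 to 13).

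**Endpoint.** Protocol section 4, RAP section 3 and RAP section 6.9 all define it as "Time to worst point on the scale or deterioration of two points or more (from randomisation) on a 9-point category ordinal scale", over Days 1-28.

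**Outputs.**
- RAP Table 10 (section 6.9) is a per-patient table. It holds the Day 1 score, the worst score, a flag headed "Deteriorated by more than 2 points (yes/no" and a column headed "Time to worst point (Days".
- SAP 12.2 plans a median and range of the "number of days to worst point on the 9-point ordinal scale". For definitions it tells the reader to "see secondary objectives in RAP for definitions".
- SAP 12.4 repeats that median and range by treatment group and adds a Kaplan-Meier plot of "Time to worst point on ordinal scale".
- In RAP 7.4, the ClinicalTrials.gov measure title and description name both parts ("Median time and range to worst point on the scale or deterioration of two points or more"). The content to be supplied is "Median and range of times to worst point on the ordinal scale".
- Protocol 13.1 and SAP section 10 also plan Kaplan-Meier plots and life tables for median survival times, and a difference with standard error for ordinal data.

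**The concern.** The definition and the outputs do not match in three ways.

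1. The two-point deterioration is half of the endpoint's wording, yet no arm-level result would show when it happens.
2. The one place that records it uses a stricter threshold than the definition printed just above it.
3. Time to worst point is undefined for a patient whose worst score is the starting score. Such a patient could be an event on Day 1, could be censored, or could be left out, and these choices give different results from the same data.

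This is the only endpoint for the clinical-improvement objective, it is planned for ClinicalTrials.gov, and Protocol 13.1 says arm differences are there only to inform later trials. In an open-label trial, a rule left unwritten may be settled after arm-level data have been seen.

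**Working it through.** The documents give no planning figure for this endpoint, so there is nothing of the plan's own to reproduce. The check is a comparison of texts followed by a small exact calculation.

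**Step 1: which outputs carry which part.**

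| Place | By arm? | Time to worst point | Two-point rise |
|---|---|---|---|
| RAP 6.9, Table 10 | No, per patient | Yes | Flag only, no day |
| RAP 6.9, Table 11 | Yes | No scale row | No scale row |
| RAP 7.4, title and description | Yes | Named | Named |
| RAP 7.4, content to be supplied | Yes | Yes | No |
| SAP 12.2 and 12.4, median and range | Yes | Yes | No |
| SAP 12.4, Kaplan-Meier | Yes | Yes | No |

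The scale listing in RAP 8.1 and the optional daily plots in SAP 12.4 give scores, not times to a two-point rise.

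**Step 2: the threshold.** 3 − 1 = 4 − 2 = 5 − 3 = 2. Each of these rises is a deterioration by the definition, and none exceeds 2, so the flag as labelled reads no. From a Day 1 score of 1, the missed move is from ambulatory to hospitalised without oxygen.

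**Step 3: the rule for patients who never worsen.** RAP section 3, to which SAP 12.2 points, only repeats the endpoint sentence. The conventions in RAP 6.10 do not cover it. SAP 11.2 covers missing values, and a patient whose worst score equals the starting score is not missing. Protocol 13.1 and SAP section 10 name Kaplan-Meier without an event or a censoring rule. Nothing visible says which day counts if the worst score lasts several days.

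**Step 4: what the missing rule does to the plot.** Assumptions (not in the documents): a proportion p worsens, and the first worst day is uniform on the 13 days from Day 2 to Day 14, with the same timing in both arms. Expected share not yet at worst at Day 7:
- Non-worseners are events on Day 1: S(7) = p(14 − 7)/13 = 7p/13.
- Non-worseners are censored: S(7) = 1 − p(7 − 1)/13 = 1 − 6p/13.

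| p, control vs camostat | Day 1 events | Censored |
|---|---|---|
| 10% vs 5% | 5.4% vs 2.7% | 95.4% vs 97.7% |
| 30% vs 15% | 16.2% vs 8.1% | 86.2% vs 93.1% |
| 40% vs 20% | 21.5% vs 10.8% | 81.5% vs 90.8% |
| 60% vs 30% | 32.3% vs 16.2% | 72.3% vs 86.2% |

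The first formula rises with p and the second falls. With common timing, the arm with less worsening therefore has the lower expected curve under one rule and the higher under the other, whatever the rates.

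**Step 5: the plain median.** If fewer than half of each arm worsens, the population median is Day 1 in both arms when non-worseners are placed at Day 1, and Day 28 in both when they are placed at Day 28. At 60% vs 30% this no longer holds: the medians are Day 4 vs Day 1 under the Day 1 placement (0.40 + 0.60 × 3/13 = 0.54 reached by Day 4) and Day 12 vs Day 28 under the Day 28 placement (0.60 × 11/13 = 0.51 reached by Day 12).

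**Step 6: precision of a two-point output**, with 50 per arm (the planned maximum), SE = √[p₁(1 − p₁)/n + p₂(1 − p₂)/n]:
- If every worsener rises two points or more, 30% vs 15%: difference −15 points, SE = √(0.0042 + 0.00255) = 8.2 points.
- If half of the worseners rise only one point, 15% vs 7.5%: −7.5 points, SE 6.3.
- 10% vs 5%: −5 points, SE 5.2.

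**The case against.** The best defence has four parts. The endpoint joins its two parts with an *or*, and SAP 11.1, 12.2 and 12.4 consistently take the first. The correct flag can be rebuilt from the Day 1 and worst scores in Table 10 itself. The planned Kaplan-Meier medians and life tables can carry censoring, and choosing Kaplan-Meier fits censoring non-worseners at least as well as calling them Day 1 events. The endpoint is secondary with no significance testing planned in Protocol 13.1, and hospital admission, oxygen-free days and ventilator-free days cover part of the same deterioration.

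Most of this stands, and it limits the point. It does not explain why the ClinicalTrials.gov entry promises a part that its content line leaves out, why the flag contradicts its own section, or where the censoring rule is written. The plain median and range cannot carry censoring in any case.

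Three stronger conclusions are tempting and not supported:
- *The planned median cannot show prevention under any rule.* At 60% vs 30% with non-worseners at Day 28 it does (Day 12 vs Day 28). The documents give no worsening rate, so rates above one half cannot be excluded.
- *The plot will make an effective drug look worse.* That needs the Day 1 rule, which the plan does not state. What is established is only that the rule is missing.
- *The endpoint must be replaced.* Definitions and one added output are enough.

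**Conclusion.** The point holds as a defect of definition and reporting that should be fixed before analysis. Two parts rest on the text alone: the flag contradicts the endpoint for every rise of exactly two points, and no arm-level output gives time to a two-point deterioration. The third part, the missing rule for patients who never worsen, is also a matter of text. Its size is illustrative: at assumed rates of 30% vs 15%, with common uniform timing on Days 2-14, the Day 7 share not yet at worst is 16% vs 8% or 86% vs 93% depending on the rule. The reversal of direction does not depend on those particular rates, but it does assume similar timing in the two arms. The primary safety outcome and the sample size are not affected.

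**What to change.** (a) Relabel the Table 10 flag as deterioration by 2 or more points (yes/no), and add the day of the first such deterioration.

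(b) Add, by arm, a Kaplan-Meier curve and life table of time from randomisation to the first rise of 2 or more points. Count death as an event, and censor patients without an event at Day 28 or last assessment. Give the Day 28 proportion with difference and SE. Measure the rise from the score at or last before randomisation: the protocol's schedule of assessments puts randomisation in the screening column and appears to mark a scale assessment there. Report it in the efficacy and intention-to-treat populations, both of which SAP 11.1 already names.

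(c) If time to worst point is kept, censor patients who never rise above baseline rather than counting them as Day 1 events, and use the first day the worst score is reached. Report the Kaplan-Meier median in place of the plain median and range. That median may not be reached, so also show the worst score as a distribution by arm.

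(d) Align RAP 7.4 and SAP 12.2 and 12.4 with these definitions. Replacing the protocol endpoint is optional.

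**Cost.** Some reprogramming and RAP/SAP wording, using scores already scheduled (daily on Days 1-14, then Days 21 and 28). The flag is a label change. The changes should be dated before any arm-level summary of the scale is run. Two limits remain. A two-point rise means different things from different baselines: a patient at 2 admitted without oxygen is not an event, while an inpatient at 3 must reach 5. After Day 14, event days are known only to an interval unless hospital or primary care records supply them.

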13 VALIDATION AND QC

The statistical report will be read and sense-checked.
